# 6.3.5. Blinding and unblinding

Data from Cohort 1 will be collected in an observer-blind manner. The participant, the site and sponsor personnel involved in the clinical evaluation of the participants are blinded while other study personnel may be aware of the treatment assignment. To do so, study intervention(s) will be prepared and administered by qualified study personnel who will not participate in the evaluation and review of any study endpoint (i.e., reactogenicity, safety).

Refer to SPM regarding details of the tasks that can be performed by the unblinded study personnel.

The laboratory in charge of sample testing will be blinded to the study intervention assignment. Codes will be used to link the participant and study to each sample. There will be no link between the study intervention groups and the identity of the participant.

The study will be conducted in an observer-blind manner for Cohort 1 from study start-up to Day 31 analysis, beyond which the study will be considered single-blind. The study participants in Cohort 1 will remain blinded up to study end, however, the investigators will receive a copy of the CSR with results of the Day 31 analysis on immunogenicity, reactogenicity and safety data. As a consequence, the investigators could become unblinded to some specific participants through summary results. The individual data listings and participant treatment assignments will not be provided to the investigators until after the conclusion of the study (completion of Visit 4, Month 12 [study end]).

Note that the GSK central study team (CRDL, Statistician, Safety Representative, etc.) will be unblinded to the study intervention assignment at the time of Day 31 analysis in order to prepare the CSR of the Day 31 analysis.

A participant may continue in the study if that participant's intervention assignment is unblinded.

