## 6.3.5.1. Emergency unblinding (Amended: 25 May 2023)

Unblinding a participant's individual study intervention number should occur ONLY in case of a medical emergency when this information is essential for the clinical management or welfare of the participant.

In case of emergency, the investigator can have unrestricted, immediate and direct access to the participant's study intervention information via an automated internet-based system (e.g., SBIR). The investigator may contact a GSK Helpdesk (refer to Table 6) if help is needed to access the participant's study intervention information (i.e., if the investigator is unable to access SBIR).

A physician other than the investigator (e.g., an emergency room physician) or participant/participant's caregiver or family member may also request emergency access to the participant's study intervention information either via the investigator or investigator's back-up (preferred option) or via the GSK Helpdesk (back-up option). The participant card provides contact information for the investigator(s), their back-up and GSK Helpdesk.

GSK's Global Safety staff may unblind the intervention assignment for any participant with an SAE. If the SAE requires that an expedited regulatory report be sent to one or more regulatory agencies, a copy of the report, identifying the participant's intervention assignment, may be sent to investigators in accordance with local regulations and/or GSK policy.

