#### 6.3.5.2. Unblinding prior to regulatory reporting of SAEs

GSK Global Safety staff may unblind the intervention assignment for any participant with a SUSAR. GSK Global Safety is responsible for unblinding the study intervention assignment within the timeframes defined for expedited reporting of SAEs (refer to Section 10.3.10.1). For SAEs requiring expedited reporting to 1 or more regulatory agencies, a copy of the report containing participant's intervention assignment may be sent to investigators in accordance with local regulations and/or GSK policy. GSK policy requires unblinding of any unexpected SAE which is attributable/suspected to be attributable to the study intervention(s), prior to regulatory reporting.

GSK policy requires unblinding of any unexpected SAE which is attributable/suspected to be attributable to the study interventions, prior to regulatory reporting. VCSP is responsible for unblinding the study intervention assignment within the timeframes defined for expedited reporting of SAEs (refer to Section 10.3.10.1).

In addition, GSK VCSP staff may unblind the intervention assignment for any participant with a SUSAR or a SAE that is fatal or life-threatening. For SAEs requiring expedited reporting to 1 or more regulatory agencies, a copy of the report containing participant's intervention assignment may be sent to investigators in accordance with local regulations and/or GSK policy.

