# 9.2. Analysis sets

Analysis sets are presented in Table 15.

Table 15 Analysis sets

Analysis set	Description
Screened Set	All participants who were screened for eligibility.
Enrolled Set	All participants who entered the study (who were randomized or received study intervention or underwent a post-screening study procedure).  NOTE: screening failures (who never passed screening even if rescreened) and participants screened but never enrolled into the study (met eligibility but not needed to reach the target enrollment) are excluded from the Enrolled Set as they did not enter the study.
Exposed Set	All participants who received the study intervention. Analysis per group is based on the administered intervention.
Per-Protocol Set*	All eligible participants who received the study intervention as per protocol, had immunogenicity results pre- and post-dose, complied with blood draw intervals, without intercurrent conditions that may interfere with immunogenicity and without prohibited concomitant medication/vaccination. Analysis per group is based on the administered intervention.

\* Contribution of participants to PPS will be defined by timepoint.

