SAP Amendment 2	15 May 2023	Final: 26 July 2022	Section 3.1.3: Addition of elimination code 1060 “Randomization code was broken”.	Section 3.1.3: Elimination code was added to eliminate participant whose randomization was broken from PPS
SAP Amendment 3	28 Feb 2024	Final: Amendment 1: 25 May 2023	Section 3.1.3: Change visit specification for elim code 1060.	Section 3.1.3: Participants having elim code 1060 will be eliminated

SAP Version	Approval Date	Protocol Version (Date) on which SAP is Based	Change	Rationale
			
Section 4.3.2.1: Change in tabulation of solicited event duration and number of days with Grade 3 solicited events.
 
Addition of specific analysis for Demyelinating disorder
 
Add sentences to clarify 6 months = 183 days.
 
Section 6.2.3.9: Addition of the definition of duration of solicited AE.
	
from a specific visit (at which the condition is met) onwards.
 
Section 4.3.2.1 & Section 6.2.3.9: Change following project update for the definition of duration of solicited symptoms.
 
Addition of specific analysis for Demyelinating disorder following project update
 
Add clarification for the number of days considered in 6 Months safety follow-up.

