3.1.3. Elimination from PPS

A participant will be excluded from the populations for analysis under the following conditions:

- For codes 800, 900, 1030, 1050, 1070, 1080, 1090, 1100 and 2010: participants will be eliminated for all visits.
- For codes 1040, 1060, 2040 and 2050: participants will be eliminated from a specific visit (at which the condition is met) onwards.
- For codes 2020, 2090, 2100, 2120: participants will be eliminated at the specific visit at which the condition is met.

Table 2 List of elimination codes

Code	Condition under which the code is used	Visit / Contact (timepoints) where the code is checked	Applicable for analysis set/endpoint
800	Fraudulent data	All	Enrolled Set, ES, PPS
900	Invalid informed consent	All	Enrolled Set, ES, PPS
1030	Study intervention not administered at all	All	ES, PPS
1040	Administration of concomitant vaccine(s) forbidden in the protocol: 
 • Use of any investigational or non-registered vaccine other than the study intervention during the period beginning 30 days before the dose of study intervention, or planned use during the study period. • Planned or actual administration of a vaccine not foreseen by the study protocol in the period starting 30 days before and ending 30 days after the dose of study intervention administration, with the exception of inactivated and subunit influenza vaccines or COVID-19 vaccines (fully licensed or with EUA) which can be administered up to 14 days before or from 14 days after the study intervention administration. * • Previous vaccination with an RSV vaccine, including investigational RSV vaccines. 	All	PPS

Code	Condition under which the code is used	Visit / Contact (timepoints) where the code is checked	Applicable for analysis set/endpoint
1050	Randomization failure: participant not randomized in the correct stratum	Visit 1	PPS
1060	Randomization code was broken	All	PPS
1070	Vaccine administration not according to protocol: 
 • Participant was vaccinated with the correct vaccine but containing a lower volume • Wrong replacement or study vaccine administered (not compatible with the vaccine regimen associated to the treatment number) • Route of the study vaccine is not intramuscular • Wrong reconstitution of administered vaccine 	Visit 1	PPS
1080	Vaccine administration after a temperature deviation Vaccine administered despite a Good Manufacturing Practices (GMP) no-go temperature deviation	Visit 1	PPS

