4.8. Changes to Protocol Defined Analyses

There were no changes or deviations to the originally planned statistical analysis specified in the protocol (Dated: 26-JUL-2022).

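### Code-break exclusion (SAP code 1060) can remove participants from the Per-Protocol Set in blinded Cohort 1 but, in practice, never in the open-label OA-RSV comparator, and SAP 4.8 does not declare it

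*SAP*

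**What the plan says.** - **The rule.** SAP 3.1.3, Table 2, lists code 1060, "Randomization code was broken", as a reason for elimination from the PPS only, checked at all visits. On timing: "For codes 1040, 1060, 2040 and 2050: participants will be eliminated from a specific visit (at which the condition is met) onwards".
- **Its origin.** The SAP version history shows the code entering with SAP Amendment 2 (15 May 2023), with the rationale "Elimination code was added to eliminate participant whose randomization was broken from PPS". SAP Amendment 3 (28 February 2024) changed its visit scope.
- **The protocol's PPS.** Protocol 9.2, Table 15, asks for eligible participants dosed per protocol, with pre- and post-dose results and compliant blood-draw intervals, "without intercurrent conditions that may interfere with immunogenicity and without prohibited concomitant medication/vaccination". Neither this definition nor the elimination criteria in 9.2.1 mention unblinding. The PPS definition in SAP section 3 does not either. Protocol 6.3.5 allows an unblinded participant to stay in the study.
- **Declared changes.** SAP 4.8: "There were no changes or deviations to the originally planned statistical analysis specified in the protocol". It cites the protocol of 26 July 2022, although SAP Amendment 3 is based on Protocol Amendment 1.
- **Blinding.** Cohort 1 is randomized and observer-blind until the Day 31 analysis. Cohort 2 (OA-RSV) is a single open-label group, all assigned to vaccine. For the assays, "The laboratory in charge of sample testing will be blinded to the study intervention assignment".
- **Routes to a code break.** Under protocol 6.3.5.1, the investigator may unblind only in a medical emergency, and sponsor safety staff "may unblind the intervention assignment for any participant with an SAE". Protocol 6.3.5.2 adds that sponsor pharmacovigilance staff "may unblind the intervention assignment for any participant with a SUSAR or a SAE that is fatal or life-threatening".
- **Back-up analysis.** SAP 4.2.2 adds an analysis on the Exposed Set (ES) if more than 5% of vaccinated participants with serology are excluded from the PPS in any group. Code 1060 does not remove anyone from the ES.

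**The concern.** Each primary hypothesis compares a Cohort 1 vaccine group with OA-RSV. An exclusion that can operate in only one of the two groups makes the PPS differ between them by construction. This one is also related to health, because the documented reasons for breaking a code are emergencies and serious events. A Cohort 1 participant with such an event may leave the PPS, while an OA-RSV participant with the same event stays.

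If people with early serious events respond less well, removing them raises the Cohort 1 seroresponse rate (SRR) and geometric mean titre (GMT), and both shifts favour non-inferiority. A code-break exclusion can make sense where knowledge of treatment could affect later dosing or a subjective rating. Here there is one dose on Day 1 and a serum titre read blind, so neither applies.

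**Working it through.** **Who can meet the condition.** Cohort 1 is randomized 2:1 and blinded, so a code can be broken. Cohort 2 is assigned to vaccine without randomization between treatments, and the protocol glossary says that an open-label study uses no blind. Table 2 does not limit the code to Cohort 1; the restriction is an inference from the design.

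**Which analyses it reaches.** Removal starts at the visit of the break, so only breaks up to Visit 2 (Day 31) affect H1 to H4. Later breaks affect only the Month 6 and Month 12 comparisons.

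**Planned size.** 342 evaluable / (1 − 0.10) = 380 per vaccine group, and 3 × 380 + 2 × 190 = 1520. Both plan figures reproduce, and code 1060 does not alter them.

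**The 5% trigger.** 0.05 × 380 = 19. More than 19 exclusions in a fully enrolled group, under all codes together, are needed before the ES analysis runs.

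**SRR shift.** Inputs: n = 342 (SAP section 5). Assumptions, because the documents give no figures: k = 2 to 4 breaks by Visit 2 in one Cohort 1 vaccine group; q = 0 to 40% responders among them; p = 0.67 to 0.77 responders among those kept. The shift from excluding them is

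p − (342p + kq)/(342 + k) = k(p − q)/(342 + k)

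| p | k | q | Shift (points) |
|---|---|---|---|
| 0.77 | 2 | 0.40 | 0.22 |
| 0.77 | 4 | 0 | 0.89 |
| 0.67 | 2 | 0.40 | 0.16 |
| 0.67 | 4 | 0 | 0.77 |

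**Error of the SRR test at the margin.** Take true rates of 0.77 (OA-RSV) and 0.67 (Cohort 1), a deficit of exactly 10 points, and the normal approximation:

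SE = √[(0.77 × 0.23 + 0.67 × 0.33)/342] = √(0.3982/342) = 0.0341

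Error = 1 − Φ(1.96 − shift/SE)

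- Shift 0.16 points: 1 − Φ(1.91) = 2.8%
- Shift 0.22 points: 1 − Φ(1.90) = 2.9%
- Shift 0.77 points: 1 − Φ(1.73) = 4.2%
- Shift 0.89 points: 1 − Φ(1.70) = 4.5%

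The nominal rate is 2.5%. The 0.67 rows are the consistent pairing with this margin scenario; using the 0.77 shifts as well extends the top of the range to 4.5%.

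**Milder assumption.** With 60 to 70% responders among those removed and p = 0.77, the shift for 2 to 4 breaks runs from 2 × 0.07/344 = 0.04 to 4 × 0.17/346 = 0.20 points.

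**GMT ratio.** If 1% of a group is removed and their titres are 4-fold lower (assumption), the ratio moves by a factor of 10^(0.01 × log10 4) = 1.014, against a margin of 1.5.

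**The case against.** The strongest reply is that this hardly matters.

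- **Few breaks are likely by Day 31.** Investigator unblinding is confined to emergencies and sponsor unblinding is permissive. The documents do not say whether sponsor safety unblinding counts as a code break under 1060. This stands, and the count of 2 to 4 has no source in the documents.
- **Code 2050 overlaps.** It may already remove participants in every group, OA-RSV included, whose condition can alter the immune response. Those lost to 1060 alone may respond nearly normally, which is the milder case above. The direction of bias is therefore conditional. This also stands.
- **The ES analysis is a safeguard.** It does keep these participants, but a few breaks would not trigger it, and it only complements the PPS result.
- **The rule was disclosed.** The version history gives its date and reason, and other Table 2 codes also go beyond the protocol's PPS wording. A reader might infer from SAP 4.8 that the change was concealed; the version history does not support that. The gap is that 4.8 does not list it.

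A reader might also take the differing unblinding provisions in protocol 6.3.5.1 and 6.3.5.2 as part of this defect. Both are permissive, and the second concerns unblinding before regulatory reporting. Reconciling them is a separate drafting point.

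**Conclusion.** The concern holds as a minor point. Code 1060 is a one-sided, health-related exclusion from the primary analysis set. It is absent from the protocol's PPS criteria, undeclared in SAP 4.8, and without benefit for a blinded laboratory endpoint after a single dose.

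Its size is probably small. The figures of about 0.2 to 0.9 SRR points and 2.8 to 4.5% error are upper-end scenarios. They assume 2 to 4 breaks by Visit 2 in one group, few responders among those removed, and a true difference exactly at the SRR margin. They describe the SRR test alone; each objective must also pass on the GMT ratio, so the error of the full claim cannot be larger. With no breaks by Visit 2, there is no effect on H1 to H4.

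Two stronger readings are tempting:

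- **That the error rate nearly doubles.** A full 1-point bias would give 1 − Φ(1.96 − 0.01/0.0341) = 4.8%, but even the worst scenario here, four breaks with no responders, reaches only 0.89 points.
- **That Month 6 and Month 12 conclusions are compromised.** With 19 breaks (5% of 380) by Month 12, the shift at p = 0.77 would be 19 × 0.37/361 = 1.9 to 19 × 0.77/361 = 4.1 points. That count is assumed, and SAP 4.3.2.2.1 makes these comparisons descriptive, so no hypothesis test depends on them.

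**What to change.** 1. Do not apply code 1060 to the neutralization-titre endpoints. List code breaks by group and by visit instead.
2. If the code is kept, justify it, define what counts as a break (in particular, whether sponsor safety unblinding does), and repeat the H1 to H4 analysis with these participants included, whether or not the 5% trigger is met.
3. In either case, make SAP 4.8 accurate: if the rule stays, record it there as a change from the protocol's PPS definition, and cite the current protocol version.

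The cost is SAP wording, one listing and, at most, one re-run of existing programs. The planned 380 enrolled and 342 evaluable per vaccine group do not change.

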4. STATISTICAL ANALYSES

4.1. General Considerations

4.1.1. General Methodology

- For the purpose of immunogenicity analyses, any missing or non-evaluable immunogenicity measurement will not be replaced. The descriptive analysis performed for each assay at each time point will exclude participants with a missing or non-evaluable measurement.
- The mean geometric increase (MGI) is defined as the geometric mean of the within-participant ratios of the post-vaccination titer over pre-vaccination (Visit 1, Day 1).
- Titers below the assay cut-off (LLOQ) will be replaced by half the assay cut-off (LLOQ/2) and titers above the upper limit of quantification (ULOQ) will be replaced by the ULOQ to compute GMTs, SRRs and MGIs. For the display of reverse cumulative curve, titers below LLOQ and above ULOQ won't be replaced.
- Confidence intervals (CIs) will use 95% confidence levels unless otherwise specified (e.g., primary endpoints analysis, refer to Section 4.2.2). 95% CIs for GMT and MGI will be based on a back transformation of CI for the mean of \log_{10} -transformed values. Exact 95% CIs around proportions are derived using the method of Clopper and Pearson [Clopper, 1934]. 95% CI for group difference in proportion will be based on Miettinen and Nurminen confidence interval [Miettinen, 1985].
- Unless otherwise specified, continuous data will be summarized using descriptive statistics: n, mean, standard deviation, median, minimum, and maximum. Categorical

data will be summarized as the number and percentage of participants in each category.

- For the purpose of displays based on the ES, in the exceptional case of a participant belonging to the OA stratum and receiving placebo (e.g., due to wrong stratification), the participant will be excluded from ES summaries.

4.1.2. Baseline Definition

For all endpoints the baseline value will be the latest pre-dose assessment with a non-missing value, i.e., the assessment at Visit 1 (Day 1).

Unless otherwise stated, if baseline data is missing no derivation will be performed and baseline will be set to missing.

4.2. Primary Endpoint(s) Analyses

4.2.1. Definition of endpoints

RSV-A and RSV-B neutralizing group GMT ratios at 1 month after the RSVPreF3 OA investigational vaccine administration will be computed for OA-RSV over Adults-HA-RSV group and OA-RSV over Adults-AIR-RSV group.

RSV-A and RSV-B neutralizing group SRR differences at 1 month after the RSVPreF3 OA investigational vaccine administration will be computed for OA-RSV over Adults-HA-RSV group and OA-RSV over Adults-AIR-RSV group.

4.2.2. Main analytical approach

The primary analysis set will be the PPS. If, in any group, the percentage of vaccinated participants with serological results excluded from the PPS is more than 5%, a second analysis based on the ES will be performed to complement the PPS analysis.

Considering the sampling timepoint at 1-month post-study intervention administration:

- The 2-sided 95% and 97.5% CIs for group GMT ratios (OA-RSV over Adults-HA-RSV group and OA-RSV over Adults-AIR-RSV group) will be derived from an ANCOVA model on \log_{10} -transformed titers for each neutralization assay. The model will include the group and the baseline \log_{10} -transformed titer as covariate. The group GMT ratios will be based on a back transformation of group contrast in the ANCOVA model applied to the logarithmically transformed titers.
- The SRR is defined as the proportion of participants having a fold increase in neutralizing titers (1-month post-study intervention administration over pre-vaccination) ≥ 4 . The 2-sided 95% and 97.5% CIs for group SRR difference (OA-RSV minus Adults-AIR-RSV group and OA-RSV minus Adults-HA-RSV group) will be derived using the method of Miettinen and Nurminen [[Miettinen, 1985](#)].

Success criteria for NI:

NI for each primary objective will be claimed if the upper limit of the 2-sided CI for the GMT ratio will be ≤ 1.5 and the upper limit of the 2-sided CI for the SRR difference will be ≤ 0.10 , according to the significance level provided by the graphical testing procedure detailed in Section 2.1. The RSV-A and RSV-B neutralizing titer's unit used for computation of the GMT ratio and SRR difference will be ED60. Refer to Section 2 for the definition of null and alternative hypotheses associated to each primary NI objective.

